Study Rationale	Adolescent alcohol exposure is associated with heightened automatic responses to stimuli that impede execution of goal-directed actions, and such behavioral inflexibility is a risk factor for alcohol and other substance use disorders. In this pilot study, we aim to determine the feasibility of delivering a 4-week online training of Koru mindfulness to freshman college students, in addition to a pre- and post-visit. Mindfulness meditation is known to reduce automatic responses to stimuli; however, it's unknown whether mindfulness training can increase behavioral flexibility in emerging adults with adolescent alcohol exposure. Young college adults experience demanding academic and social schedules that challenge maintenance of healthy behaviors while learning to adapt to emerging adulthood. Mindfulness training is one strategy to support healthy outcomes that persist despite inevitable stressors.
Study Objective(s)	
Primary
 
 • To determine the feasibility of subject recruitment, participant retention, visit attendance, and study design among freshman college students. 
Secondary
 
 • To assess participant satisfaction with study procedures.
Test Article(s) (If Applicable)	Koru Mindfulness Training
Study Design	This is a parallel assignment randomized controlled trial feasibility study. The two-armed study has the mindfulness meditation intervention and the control groups running parallel to one another. Participants are blinded to condition.
Subject Population key criteria for Inclusion and Exclusion:	
Inclusion Criteria
 
 • College enrolled first-year students aged 18-19 years old • Internet access to enable online training • Fluent English speaker (\leq age 7) • ≥ 4 lifetime binge drinking episodes • Meditation-naïve 
Exclusion Criteria
 
 • Subjects with known neurological, psychiatric, or systemic disease • Subjects with any type of motor or visual disturbance that may interfere with performing the cognitive task • Subjects using psychoactive drugs (aside from moderate caffeine or alcohol) or medications • Subjects with a known history of any substance use disorder (not including alcohol or nicotine) or desire to seek treatment for excess substance use
Number Of Subjects	18

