Study Duration	
 • Each subject will undergo 4 weeks of intervention or control group training, a pre- and post-training visit, and a 1-month follow-up. • The entire study is expected to last 3 months.
Study Phases	(1) Subjects screened for eligibility and obtaining consent;
Screening	(2) Cognitive task performance, blood sample collection, surveys;
Study Treatment	(3) Four weeks of virtual training in Koru mindfulness or an age- and time-matched comparison group;
Follow-Up	(4) One-month follow up online surveys
Efficacy Evaluations	
 • Mean number of visits attended by participants and total number of journal entries.
Pharmacokinetic Evaluations	N/A
Safety Evaluations	Self-report measures of anxiety, depression, and stress will be evaluated at the beginning of each visit to determine any changes that could be in result of the intervention.
Statistical And Analytic Plan	
 • To assess the primary objective (feasibility) of the study, the primary outcome will be the count of participants in each of the 6 visits, and the number of surveys that are completed at the 1-month follow-up contact. • To assess the secondary objective (participant compliance), the secondary outcome will be measured by total journal entries submitted during the 4 weeks of intervention training.
DATA AND SAFETY MONITORING PLAN	The Co-Investigators will review participants' experiences with study procedures on a weekly basis. Meditation practice may elicit discomfort if traumatic memories resurface or the participant is experiencing high stress. The Koru teacher is trained in trauma-sensitive mindfulness and has implemented this awareness in the design of the visits. Nonetheless, the teacher will regularly check in with students to address any concerns.

BACKGROUND AND RATIONALE

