4.2 Intervention procedures (by visits)

See Figure 1 for overview of study visits.

Visit 1

- Written consent, MINI interview [25], urine drug screen and breathalyzer alcohol test, C-reactive protein (CRP) assay, Reward-AB task

Visits 2-5

- Randomization to either the Koru Mindfulness (KM) intervention or the Navigating College (NC) control group.
- Each training visit will consist of the following:
 - Surveys completed online through REDCap.
 - 75 minutes of instructor-led discussion
 - Breakout sessions for participants to share their thoughts and experiences in response to instructor's prompt.

Navigating College (NC) Control Group Training

Topics discussed during each training visit include: habits, roommate issues, homesickness, the internet (week 1); strategies when sinking, study skills, getting involved, habit formation (week 2); HALT, gateway habit (week 3); and academic success tips, taking notes, and procrastination (week 4).

Koru Mindfulness (KM) Intervention Training

Topics discussed during each training visit include: belly breathing, dynamic breathing, body scan (week 1); walking meditation, gatha (week 2); guided imagery, labeling thoughts (week 3); eating meditation, and labeling feelings (week 4).

Daily Logging of Skills

Participants in the CG intervention will be asked to journal by hand or via Qualtrics every day for ≥ 10 minutes, on anything related to the topics learned during that week's training visit. Participants in the KM intervention will

be asked to practice every day for ≥ 10 minutes any mindfulness or meditation skill previously learned during training visits, in addition to logging their practice and reflection using the Koru application.

Visit 6

- Similar to visit 1, without repeating the MINI interview.

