6.1 Primary Endpoint

1. Feasibility assessment [Time Frame: every week]
 - a. The feasibility of the study design will be measured using the total number of eligible participants, and retention rate for each visit, in addition to the one-month follow-up survey of enrolled participants. Compliance with individual training will be determined by the mean number of journal entries submitted per week in each group, due to previous evidence demonstrating an association between amount of homework completed and positive outcomes [40].

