6.3 Statistical Methods

The total number of eligible participants will be used as a measure of successful recruitment strategies and feasibility of enrollment criteria. The mean number of self-report training or journaling days recorded by participants and the total number of visits attended by each participant will be used as measures of compliance with study procedures. The number of times discomfort is reported by participants with any training procedure will be used as a measure of safety. A within-subjects ANOVA will be used to analyze the change in DASS-21 scores across the training visit weeks, including the total score and scores for all 3 subscales. A 1-Sided t-Test will be used to analyze the mean difference in CEQ score between the intervention and control group.

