8.1 Administration for Training Groups

After Visit 1, participants will be randomized to either the intervention or control group using a randomized number computer generator (e.g., 01-18 assigned to mindfulness meditation group). The NC and KM training instructor will be blinded to the group each participant is randomly assigned to, and participants will be assigned a unique ID to put as their name for their Zoom profile and on questionnaires. This number will be given (and recorded) by a research assistant. During training visits, all videos (except the instructor's) will be turned off.

SAFETY MANAGEMENT

We do not anticipate participant safety to be an issue in this study. Proposed procedures do pose a risk of harm if safety protocols are not followed carefully. To ensure participant safety, all participants will be thoroughly screened by trained personnel for the presence of conditions that could pose a threat to the subject. All research personnel will be trained in blood collection by finger prick. Daily practice logs will give participants a safe space to share any discomfort experienced during training. If participants in the KM group are experiencing extreme discomfort during weeks when visits 2-6 take place, due to resurfacing of traumatic experiences, subjects will be withdrawn from the study and given resources to alleviate distress. Logs will be checked daily. Any adverse event related to the training or blood collection will be immediately reported to the Principal and Co-Investigators.

DATA COLLECTION AND MANAGEMENT

We will obtain a certificate of confidentiality for this study. A participant's personal information could be linked with their study data. To minimize this risk, no one outside of the research team will have access to participants' data. Participants' data will only be identified in all computer analyses with their ID numbers. Any paperwork that includes participants' names or other personal information will be stored in a locked file cabinet in the locked lab. All data will be archived without personal identifiers, using only ID numbers. Emails to participants will be encrypted.

RECRUITMENT STRATEGY

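### Section 6.3 analyses DASS-21 change over the training weeks without comparing the arms, so it cannot separate an effect of the training from a trend that both groups share

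*Combined protocol and SAP*

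**What the plan says.** The synopsis (Safety Evaluations) gives this purpose for the questionnaires on mood and stress: "evaluated at the beginning of each visit to determine any changes that could be in result of the intervention". It does not name the instrument. Section 5.4 does: DASS-21, given at the start of each visit, with within-subject changes prompting further review. Section 6.2 lists DASS-21 as a secondary endpoint with an 8-week time frame.

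Section 6.3 contains the only analysis: "A within-subjects ANOVA will be used to analyze the change in DASS-21 scores across the training visit weeks", applied to the total and the three subscales. Arm is not mentioned.

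Arm is mentioned for other outcomes. Section 6.1 uses "the mean number of journal entries submitted per week in each group", and 6.3 itself tests "the mean difference in CEQ score between the intervention and control group".

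On design, the synopsis says: "The two-armed study has the mindfulness meditation intervention and the control groups running parallel to one another". Section 3.2 randomises 18 students, 9 to each group, at the end of visit 1. Section 7.1 (Navigating College) matches the control training to the mindfulness training on duration, class structure and instructor.

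**The concern.** The two groups pass through the same weeks of their first college year. Coursework pressure could raise DASS-21 scores in everyone, and settling in could lower them. A repeated-measures test of time alone responds to either, whether or not the training has any effect. Given the purpose stated in the synopsis, a significant time effect could be taken as a consequence of mindfulness training. A null result could equally be taken as reassurance when the arms had moved in opposite directions. The randomised, matched control group is there to remove this ambiguity, and the DASS-21 analysis as written does not use it.

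What is at stake is the meaning of the DASS-21 result when it informs the larger study that 2.1 has in view.

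**Working it through.** The plan gives no alpha, SD, effect size or power for DASS-21, and 6.4 declares a power analysis not applicable, so there is no stated figure to reproduce. The main check is textual; the arithmetic shows its size.

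**Structure, from the plan alone.** With 9 students per arm, the pooled mean change is (9 × KM + 9 × NC)/18, where KM and NC are the mean changes in the mindfulness and control arms.
- A rise of 0.5 SD in one arm only gives 0.25 SD pooled, whichever arm it is.
- A rise of 0.25 SD in both arms also gives 0.25 SD.
- A rise of 0.5 SD in one arm and a fall of 0.5 SD in the other give 0.

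**Illustration.** Assumptions not in the plan: all 18 scored at visits 2 to 5, nobody withdrawn, total SD 1, linear change of d SD from first to last training visit, equal within-person correlation ρ of 0.5, 0.7 or 0.8, alpha 0.05.

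*Pooled ANOVA, both arms rising by d.* The four visit means are 0, d/3, 2d/3 and d, so the sum of squared deviations from their mean is 2d²(1/4 + 1/36) = 0.556d². The noncentrality is λ = 18 × 0.556d²/(1 − ρ) = 10d²/(1 − ρ), with 3 and 51 df.

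| d | λ at ρ = 0.5, 0.7, 0.8 | Proportion significant |
|---|---|---|
| 0.3 | 1.8, 3.0, 4.5 | 0.166, 0.256, 0.373 |
| 0.5 | 5.0, 8.3, 12.5 | 0.411, 0.637, 0.826 |

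For d = 0.5 in both arms, an arm-by-visit F test (3 and 48 df; 20,000 simulated trials per case) is significant in 0.052, 0.048 and 0.049.

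*Separate ANOVA in each arm, same shared rise of 0.5 SD.* Now n = 9, so λ = 5d²/(1 − ρ) = 2.5, 4.17, 6.25 with 3 and 24 df. Each arm is significant with probability p = 0.203, 0.321, 0.466. Exactly one arm is significant with probability 2p(1 − p) = 0.324, 0.436, 0.498. So even when the arms change identically, about a third to a half of trials would show change in one arm and not the other. Running the test by arm does not supply the comparison.

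*Other patterns (simulation; ρ = 0.5, 0.7, 0.8).*

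| Pattern | Pooled ANOVA | Arm-by-visit |
|---|---|---|
| KM +0.5 SD, NC 0 | 0.118, 0.173, 0.240 | 0.127, 0.185, 0.263 |
| KM 0, NC +0.5 SD | 0.118, 0.169, 0.239 | not run; same by symmetry |
| KM +0.5 SD, NC −0.5 SD | 0.037, 0.030, 0.023 | 0.403, 0.639, 0.826 |

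**Precision of the replacement.** For the between-arm difference in change between two visits, the 95% half-width is t(0.975, 16) × √(2(1 − ρ)) × √(2/9) = 2.12 × √(2(1 − ρ)) × 0.471. This gives 1.00, 0.77 and 0.63 SD for ρ = 0.5, 0.7 and 0.8.

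**The case against.** **The plan does not say the arms are pooled.** This stands. Section 6.3 also leaves out arm for journaling days, although 6.1 reports journal entries by group, so silence in 6.3 is weak evidence of pooling. A reader might infer that all 18 students are certain to be analysed together, or that the plan makes it impossible to see where scores rose. The text supports neither: the ANOVA could be run within each arm, and allocation is recorded. But separate within-arm tests still do not compare the arms, so the gap remains on either reading.

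**The DASS-21 is there for individual monitoring.** This stands in part. Section 5.4 describes within-subject review, 6.5 acts participant by participant, and no between-arm DASS-21 hypothesis is stated. But DASS-21 is also a secondary endpoint with a group-level analysis, and the synopsis ties these measures to changes the intervention may have caused. Individual review cannot answer that.

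**Nothing depends on it.** Largely right. No go/no-go rule or sample-size calculation uses the DASS-21 result.

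**Adding arm hardly improves detection.** Also right for a one-arm rise of 0.5 SD: 13% to 26% against 12% to 24%. The gain is in attribution, which is why an estimate with an interval is proposed.

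**The arms may also report discomfort differently.** A reader might infer from 4.2 that discomfort logs differ by arm, since control students "journal by hand or via Qualtrics every day" while mindfulness students use the Koru application. But 7.1 (Koru Mindfulness) allows an application or a journal, so that contrast is too weak to build on.

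**Conclusion.** The concern holds as an analysis-choice point worth considering. The planned DASS-21 analysis contains no comparison of the arms and therefore cannot separate a training effect from a shared time trend, which is what the synopsis purpose calls for. That conclusion rests on the text alone, with the link from the synopsis to DASS-21 running through 5.4.

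The percentages are illustrations. They depend on the assumed SD scale, linearity, correlation of 0.5 to 0.8 and complete data at visits 2 to 5. The interval half-widths apply to a simple two-visit comparison with all 18 scored; withdrawals would widen them.

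A reader might infer that participants are less safe or that the feasibility result is compromised. The documents do not support that: individual review and stopping under 5.4 and 6.5 operate without this analysis, and the primary outcomes in 6.1 do not use DASS-21. Section 6.5 does not define how large a DASS-21 rise triggers stopping, but that is a separate matter of missing detail.

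**What to change.** Replace the DASS-21 sentence in 6.3 with:

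*DASS-21 total and subscale scores will be summarised by arm at each visit using all available scores, including those up to the point of any withdrawal. A mixed model (or mixed ANOVA) with arm, visit and arm-by-visit terms will estimate the between-arm difference in change from visit 1, with a 95% CI. Only this difference will be read as relating to the intervention.*

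Visit 1 is a suitable reference because randomisation follows at its end. If a mixed ANOVA with arm was intended all along, this wording makes that explicit.

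The cost is a short change of text and a small table, from data already collected. The drawback is precision: at 9 per arm the interval is about ±0.6 to ±1.0 SD under the assumptions above, so the report should present the result as an estimate for planning and not as a test of harm or benefit.

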1.2 Name and Description of Investigational Product or Intervention

Koru Mindfulness (KM) Intervention Training

The Koru Basic curriculum [18] will consist of four weekly interactive 75-minute classes delivered online through Zoom. Each class will consist of an overview of 2-3 skills, group practice of the skills, and group reflection. Class size will be limited to 9 participants. Participants will have their video off and will have their own unique identifier (instead of identification by name). Participants will be instructed to practice a skill for 10 minutes/day and log their reflection on that practice using the Koru phone application.

Navigating College (NC) Control Group Training

The control group will consist of four weekly 75-minute classes delivered online through Zoom. Each class will consist of lecture and group discussions on topics related to navigating college [19]. Participants will be instructed to journal about learned information and skills for 10 minutes/day.

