3.2 Allocation to Treatment Groups and Blinding (if applicable)

At the end of visit 1, participants will be randomly assigned to either the training group where they will learn mindfulness and meditation skills, or the control group to learn skills in navigating college. An online random number generator will be used to determine which subject IDs will be allocated to each training group (18 people total, 9 in each group).

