3.3 Study Duration, Enrollment and Number of Subjects

The entire duration of the study is expected to take no more than 3 months. About 5-6 weeks will elapse from the first visit to the 6th visit, and the inclusion of a one-month follow-up survey adds another 4 weeks, totaling a little over 2 months. Eighteen subjects are expected to be enrolled in the study, with 9 participants randomized to each of two training groups (Koru Mindfulness as the intervention training, Navigating College serving as the age- and time-matched comparison group).

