7.1 Navigating College (NC) Control Group

The NC training is designed to match the KM training in at least the total duration of the training, the duration of each individual visit, the practice of daily training of a skill, class structure, and instructor. The skills taught are directly related to the topics discussed in the *Freshman Survival Guide: Soulful Advice for Studying, Socializing, and Everything In Between* [19].

Participants will be encouraged to write in their paper journal or online (via Qualtrics) for about 10 minutes every day. Prompts with suggested topics for reflection will be provided.

STUDY INTERVENTION ADMINISTRATION

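### Each arm appears to be one class of 9, so the CEQ t-test cannot separate training from class, and it rejects too often if classmates' scores are correlated

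*Combined protocol and SAP*

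**What the plan says.** Individuals are randomised at the end of visit 1, "18 people total, 9 in each group" (section 3.2). Section 3.3 repeats the split: "Eighteen subjects are expected to be enrolled in the study, with 9 participants randomized to each of two training groups".

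Training is given in weekly live Zoom classes. In the Koru Mindfulness (KM) part of section 1.2, "Class size will be limited to 9 participants" and "Each class will consist of an overview of 2-3 skills, group practice of the skills, and group reflection". For Navigating College (NC), "Each class will consist of lecture and group discussions on topics related to navigating college". Section 4.2 adds breakout sessions in both arms. The NC part of section 7.1 lists among the features matched to KM "the practice of daily training of a skill, class structure, and instructor", and section 8.1 speaks of a single instructor for both trainings.

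For the Credibility/Expectancy Questionnaire (CEQ), section 6.3 says: "A 1-Sided t-Test will be used to analyze the mean difference in CEQ score between the intervention and control group". Section 6.2 gives CEQ a time frame of 1 week and says that it should help in designing better comparison groups. Section 6.1 measures compliance by the "mean number of journal entries submitted per week in each group", with no test attached.

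The documents give no significance level, no ICC and no mention of class as a source of variation. Section 6.4 declines a power analysis.

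**The concern.** A two-sample t-test takes its standard error from the spread among individuals within each arm. If each arm is one class, that spread is entirely within-class. Whatever moves a whole class together, such as a lively or flat group or a bad time slot, shifts the arm mean without entering the standard error. A CEQ difference caused by one such class would then be read as a property of the training.

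This matters because the CEQ result is meant to guide the choice of comparison group in later work, and it is the only between-arm test planned in 6.3.

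**Working it through.** **Inputs from the documents.** 18 people, 9 per arm (3.2, 3.3). Class cap 9 (1.2, under KM). Class structure and instructor matched across arms (7.1, NC). One-sided two-sample t-test on CEQ (6.3).

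**Assumed inputs.** One-sided level 5%, because none is stated. ICC for CEQ within a class from 0 to 0.10, because none is stated. Equal SDs and normal scores.

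**Plan's own figure.** 18/2 = 9 per arm, which agrees with the plan. There is no power figure to reproduce.

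**Step 1: number of classes.** 9 per arm divided by a cap of 9 gives 1 class per arm. One instructor cannot lead two live classes at once, so the arms would meet at different times. Arm, class and time slot then coincide.

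**Step 2: can class variance be estimated?** 2 classes minus 2 arms leaves 0 degrees of freedom. No re-analysis of these data can supply the missing component.

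**Step 3: size of the omission.** Let r be the ICC and m = 9.

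- True variance of the difference in means: 2·SD²·[r + (1 − r)/9].
- Variance that the t-test estimates: 2·SD²·(1 − r)/9.
- Ratio of the two standard errors: k = √(1 + 9r/(1 − r)).
- With no training effect, the test statistic behaves as k times a t variable on 9 + 9 − 2 = 16 df. The one-sided error rate is therefore P(t16 > 1.746/k).

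For r = 0.05: k = √(1 + 0.45/0.95) = √1.474 = 1.21, and 1.746/1.214 = 1.438, which gives 8.5%.

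| Assumed ICC | k | True SE of difference (SD units) | Error rate at assumed one-sided 5% | At assumed one-sided 2.5% |
|---|---|---|---|---|
| 0 | 1.00 | 0.471 | 5.0% | 2.5% |
| 0.01 | 1.04 | 0.490 | 5.7% | 3.0% |
| 0.05 | 1.21 | 0.558 | 8.5% | 5.0% |
| 0.10 | 1.41 | 0.632 | 11.7% | 7.7% |

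A simulation of 400,000 trials at the 5% level gave 5.0%, 8.5% and 11.6% at ICC 0, 0.05 and 0.10.

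**Step 4: if one class per arm is wrong.** With two classes of 5 and 4 in each arm, simulation gives about 5.3%, 6.6% and 8.1% at ICC 0.01, 0.05 and 0.10. The excess is smaller but does not vanish.

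**The case against.** **The inflation may be absent.** It needs a positive ICC, and the documents give none. Timing bears on this. The CEQ time frame is 1 week, and surveys open each training visit (sections 3.1 and 5). If CEQ is taken before the first class, participants have shared nothing and the ICC could be near zero. This stands, and it makes the point conditional.

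**The design limits clustering.** Individuals are randomised, the instructor and class structure are matched, cameras are off and IDs replace names. These features remove some usual sources of correlation. They do not remove correlation that arises later, from shared sessions and a shared slot.

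**The test is approximately valid for a narrower question.** Because individuals are randomised, it addresses whether assignment to these two delivered packages changed CEQ. The excess error arises when the result is read as a statement about the trainings in general. This also stands. However, using CEQ to design future comparison groups calls for the broader reading.

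**One class per arm is inferred.** No sentence says it, and the cap appears under KM only. It is the natural reading, since the arm size equals the cap, NC is matched on class structure and no second class is described. The example in section 8.1, which sends IDs 01 to 18 to mindfulness, does not fit 9 per group and should be reconciled.

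**Two stronger readings.** A reader might infer that the error rate definitely exceeds the level set in the plan. The plan sets no level, and the excess depends on an unknown ICC. A reader might also infer that the journal-entry comparison is an invalid test. No test or interval is planned for journal entries, so there the issue is only how the means are described.

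**Conclusion.** The point holds conditionally and is minor. The plan implies one class per arm, so training is confounded with class and time slot, and the CEQ t-test has no way to allow for this. Its error rate as a statement about the trainings ranges from 5.0% with no correlation to 11.7% at an ICC of 0.10. That range rests on an assumed one-sided 5% level, assumed ICCs and one class of 9 per arm. The consequence is limited because CEQ is a secondary endpoint in an 18-person feasibility pilot that makes no power claim. What should change is the conclusion that the pilot may draw: a CEQ difference describes these two classes.

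**What to change.** - **Section 6.3, CEQ.** Replace the test with arm means, SDs and the difference with an interval labelled as reflecting within-class variation only. The label is needed: from 2P(t16 > 2.120/k), a nominal 95% interval would cover about 90% at ICC 0.05 and 85% at ICC 0.10. A sensitivity range that multiplies the standard error by k (1.21 and 1.41 at those ICCs) is optional.
- **Interpretation.** State that class and training cannot be separated, so a CEQ difference describes the two classes delivered.
- **Section 6.1, journal entries.** Label the per-group means as results of two classes. Nothing else changes there.
- **Clarifications.** State how many classes each arm has and whether CEQ is collected before or after the first class.
- **Scheduling.** People who pass the phone screen are booked for every visit (Recruitment Strategy) before randomisation at the end of visit 1 (3.2), and nothing says that they can attend either slot. Confirm this before randomisation, so that availability does not decide who attends.

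The cost is some SAP wording, one screening question, a lost p-value, and possibly a few people who cannot attend both slots. Class variance itself can be estimated only in a later study with several classes per arm.
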